14.3.3 Disease activity over time

Table 23 provides details on disease activity endpoints.

Table 23 : Disease Activity Endpoints

Endpoint (*)	Analysis method	Data Handling Notes
CFB in SLEDAI-2K score	
 • Descriptive statistics for continuous variable, including absolute value, CFB and percent CFB 	As observed
CFB in CLASI-A score	
 • Descriptive statistics for continuous variable, including absolute value, CFB and percent CFB 	As observed
BICLA response	
 • Number and percentage of subject with response by each treatment group • Presentation of adjusted Odds-Ratio (OR), 2-sided 95% CI of OR, nominal p-value, adjusted p-value from Logistic Regression (same as primary analysis of primary endpoint) 	As primary analysis
CFB in BILAG-2004	
 • Descriptive statistics of total score, including absolute value at baseline and each post baseline visit, CFB and percent CFB at each post baseline visit 	As observed
CFB in PGA	
 • Descriptive statistics, including CFB and percent CFB for the PGA score as a continuous variable on a 0-3 scale 	As observed

(*) See Appendix 18.1 for definition of each endpoint.

14.3.4 HRQoL

The following HRQoL endpoints are summarized in Table 24.

All endpoints are described in Appendices 18.3, 18.4, 18.5, 18.6 and 18.7. They will be analyzed on QoL Analysis Set.

Table 24 : HRQoL analysis

Questionnaire	Score to be analyzed	Analysis Set	Analysis
SF-36 v2	Change in PCS, MCS scores, and their components	
 QoL Analysis Set 	
 Mixed model with repeated measures (MMRM) model Descriptive statistics Distribution %CFB curve Logistic regression
LupusQoL	Change in each domain score	
 QoL Analysis Set 	
 MMRM model Descriptive statistics Distribution %CFB curve
FACIT-Fatigue	Change in Total score	
 QoL Analysis Set 	
 MMRM model Descriptive statistics Distribution %CFB curve Logistic regression
EQ-5D-5L	Change in VAS score, EQ-5D-5L index	
 QoL Analysis Set 	
 MMRM model Descriptive statistics
PGIC	% of subjects with improvement, no change and worsening	
 QoL Analysis Set 	
 Logistic regression Descriptive statistics

MMRM model:

Missing data will be considered as MAR.

The QoL endpoints will be analyzed using the MMRM model, with treatment group, visit, and treatment by visit interaction as the main effects, baseline assessment and randomization strata as covariates. The unstructured covariance matrix will be considered. Denominator degree of freedom will be computed using Kenward and Roger’s method (Kenward 1997).

The LSMEAN estimate of mean change from baseline score, difference of the LS Mean from placebo, 2-sided 95% CI of the difference, and nominal 2-sided p-value of the difference from the model contrast will be presented.

An example of SAS code is available in Appendix 18.9.

Descriptive statistics:

For each treatment group, descriptive statistics will be presented for absolute value, CFB and percent CFB value for each visit, from baseline to Week 52.

In addition, the following will be provided:

- Mean score CFB will be presented as a by-visit line plot for each treatment group, with all treatment groups included in a single figure, and horizontal axis extending to Week 52
- A bar-chart figure of Mean score CFB at Week 52 presenting each SF-36 sub-domain score type (PF, RP, BP, GH, VT, SF, RE, MH) for each treatment will be provided.
- For PGIC, the number (proportion) of subject of subjects with any improvement (i.e., PGIC = 1, 2 or 3), no change (i.e., PGIC = 4) and any worsening (i.e., PGIC = 5, 6 or 7) will be summarized by visit and treatment group.

Probability of achieving %CFB value or higher:

For each SF-36 endpoint (domain scores, MCS, PCS), a figure will be provided describing the distribution of % CFB at Week 52, one curve per treatment group. The curve will display proportion of subjects having a value for % CFB > x at Week 52, where the range of x depends on the data. The same will be applied for FACIT-Fatigue total score and each domain score of LupusQoL.

Logistic regression:

Response on the SF-36, FACIT-Fatigue total score and PGIC will be further analyzed based on differences in proportion of responders, comparing each dose of evobrutinib to placebo.

Responder definitions will be based on minimal clinically important difference (MCID) criteria for improvement or deterioration from baseline as follows ([Strand 2005](#), [Lai 2011](#)):

- SF-36 – PCS & MCS:
 - Improvement is defined as an increase greater or equal to 2.5 compared to baseline
 - Deterioration is defined as a decrease greater or equal to 0.8 compared to baseline
- SF-36 – domain scores:
 - Improvement is defined as an increase greater or equal to 5.0 compared to baseline
 - Deterioration is defined as a decrease greater or equal to 2.5 compared to baseline
- FACIT-Fatigue Total Score:

- Improvement is defined as an increase greater or equal to 4.0 compared to baseline
- Deterioration is defined as a decrease greater or equal to 4.0 compared to baseline
- PGIC: improvement is defined as value = 1, 2 or 3

Logistic regression model for repeated measures will be applied, with adjustments for the randomization strata, baseline value and treatment as a factor. The estimated OR at Week 52, together with associated two-sided 95% CI of the estimated OR will be presented. For PGIC improvement, results will be presented at Week 12, 24, 40 and 52 visits. An example of SAS code is available in Appendix 18.9.

14.3.4.1 Subgroup analysis

MMRM, logistic regression, distribution %CFB curves and descriptive statistics will be repeated on QoL Analysis Set for each SF-36 endpoint, FACIT-Fatigue total score and each domain score of LupusQoL according to the following subgroups:

- Screening SLEDAI-2K scores:
 - a. <10 (non-HDA);
 - b. ≥ 10 (HDA)
- Baseline severity of disease:
 - a. Severe: defined as at least one BILAG A; vs.
 - b. Moderate: defined as at least 2 BILAG B and no BILAG A; vs.
 - c. Mild: defined as 1 BILAG B and no BILAG A and no more than 1 BILAG B
 - d. No severity: defined as criteria for severe, moderate and mild not met.

14.3.5 Corticosteroid usage over time

CS usage over time will be analyzed on the mITT set using data collected in “Relevant Previous Medications Details” and “Concomitant Medications” eCRF Forms.

Only CS taken at baseline or after will be taken into account. Any CS with an end date before screening date will not be taken into account in the following analysis.

General rules, missing data handling, conversions and cumulative dose is defined in Appendix 18.8.

The following endpoints will be described for statistical analysis:

- Clinically meaningful reduction in CS dose from Baseline, defined by:
 - A reduction of daily prednisone-equivalent CS dose $\geq 25\%$ to a dose of ≤ 7.5 mg/day by Week 40 + 1 day (i.e. Week 41) and sustained through Week 52

AND

- No new BILAG A organ domain scores and no more than one new BILAG B organ domain score during Weeks 40 + 1 day (i.e. Week 41) through 52.

Subjects withdrawing from treatment before Week 40 or with missing data at Week 40 will be considered as non-responders. The analysis will be performed on the mITT subjects whose CS dose is greater than or equal to 7.5 mg at baseline.

- Change from Baseline to Week 52 in prednisone-equivalent CS daily dose.

Summary statistics for absolute value, CFB and percent CFB by visit during treatment period in prednisone-equivalent CS daily dose will be provided.

- Reduction by visit, from Baseline to Week 52, in prednisone-equivalent CS daily dose of zero to < 25%, 25% to 50%, > 50%, or an increase.

The same table will be produced with the following categories of prednisone-equivalent CS daily dose at Week 52: ≤ 6 mg, > 6 - 7.5 mg, > 7.5 – 10 mg, > 10 – 20 mg, > 20 – 30 mg and > 30 mg. The proportions are based on the observed subjects as the denominator.

- Cumulative prednisone-equivalent CS dose from Baseline until completion of the Treatment Period (absolute value only) will be described using summary statistics.

Cumulative prednisone-equivalent CS dose will be compared between placebo arm and evobrutinib arms with a pairwise non-parametric Wilcoxon rank sum test.

[figure not shown]
All CS doses will be listed for each subject and flagged for any doses not taken into account in calculation of the scheduled-visit dose (e.g. dose taken between two scheduled visits or dose with missing information). Subjects non-compliant with protocol rules on CS usage will be listed based on protocol deviation data (i.e. all subjects with PD code = PDEV52e).

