11.2 Other Baseline Characteristics

11.2.1 Disease History

SLE disease characteristics at Baseline will be presented in 4 parts according to [Table 12](#), [Table 13](#),

[Table 14](#) and [Table 15](#). Unless indicated otherwise, these characteristics will be presented according to the definition of baseline in Section [9.5](#).

For LTE analysis, the SLE disease characteristics will be produced using Baseline from 52-week treatment period and using Baseline from LTE Day 1. The CLASI total activity score (continuous and categorical) will also be produced using Baseline from 52-week treatment period and using Baseline from LTE Day 1.

The SLE disease characteristics summary at LTE Day 1 will be presented for the subjects with a gap greater than or equal to 2 weeks between 52-week and LTE treatment periods.

Table 12: SLE Disease Characteristics at Baseline

SLE Disease Characteristic at Baseline	Modality
Time (months) since confirmed diagnosis of SLE [@]	
Time will be computed as (Date of Informed Consent Signature – Date of confirmed diagnosis of SLE) / 30.4375. If the date of confirmed diagnosis of SLE is entirely missing, then time since confirmed diagnosis of SLE will not be computed. In case of partial missing date of confirmed

	
diagnosis of SLE, this date will be imputed as follows:
 
 ○ If only the day is missing, then it will be replaced by the first day of the month ○ If both day and month are missing, then it will be replaced by the first of January 
Date of Informed Consent Signature will be obtained from DEM form of the eCRF. Date of confirmed diagnosis of SLE will be retrieved from DIAG form of the eCRF.

PGA Score (Baseline)	Converted value will be presented (from SLEDAI1/SLEDAI3 form of the eCRF)
Prednisone-equivalent CS daily dose (Baseline)	Continuous
Number of subjects with prednisone-equivalent CS dose categories 1 (Baseline)	
 • ≤7.5 mg/day, • >7.5 mg/day. • Missing
Number of subjects with prednisone-equivalent CS dose categories 2 (Baseline)	
 • 0 mg/day, • > 0 to 7.5 mg/day, • > 7.5 mg/day. • Missing
Number of subjects with prednisone-equivalent CS dose categories 3 (Baseline)	
 • 0 mg/day, • > 0 to 6 mg/day, • > 6 to 7.5 mg/day, • > 7.5 to 10 mg/day, • > 10 to 15 mg/day, • > 15 to 20 mg/day, • > 20 to 30 mg/day, • > 30 mg/day. • Missing

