14.3.1 Disease Activity Endpoints

The following secondary endpoints to be analyzed on mITT analysis set are summarized in [Table 19](#). LLDAS is defined in [Appendix 18.1.7](#).

For SRI-4 and SRI-6 response endpoints as well as LDA status and LLDAS, the primary analysis method applied to the two-primary endpoints ([Section 14.1.2.1](#)) will be performed.

In addition, for LDA and LLDAS endpoints in [Table 19](#), the number and percentage of subjects with response or non-response will be summarized over time (by visit), using similar imputation rules as applied for the Week 52 timepoint.

Table 19 : Disease Activity Endpoints

Endpoint	Analysis method	Data Handling Notes

 • SRI-6 response at Week 52, in the serologically active subgroup • SRI-4 Response at Week 52 with a Sustained Reduction of OCS Dose to 7.5 milligrams prednisone-equivalent per day or less (≤ 7.5 mg/day) and less than or equal to (\leq) Day 1 dose during Week 41 Through Week 52, in all subjects • SRI-6 Response at Week 52 with a Sustained Reduction of OCS Dose to 7.5 milligrams prednisone equivalent per day or less (≤ 7.5 mg/day) and less than or equal to (\leq) Day 1 dose during Week 41 Through Week 52, in the HDA subgroup • SRI-4 Response at Week 52 with a Sustained Reduction of OCS Dose to 7.5 milligrams prednisone equivalent per day or less (≤ 7.5 mg/day) and less than or equal to (\leq) Day 1 dose during Week 41 Through Week 52, in the serologically active subgroup 	Same as the Primary Method in Table 17	Same as the Primary Method in Table 17

 • LDA status, defined by SLEDAI-2K ≤ 2 at Week 52 • LDA, defined by clinical SLEDAI-2K (SLEDAI-2K excluding anti-dsDNA and low complement parameters) ≤ 2 at Week 52 • LLDAS at Week 52 	Same as the Primary Method in Table 17	Same as the Primary Method in Table 17

In order to determine whether the subject had a sustained reduction of OCS Dose to ≤ 7.5 mg/day and \leq Day 1 dose during Week 41 Through Week 52, the daily dose of CS will be calculated for each analysis visit from Week 41 to Week 52, according to Appendix 18.8. If the condition is met for all days during this period, the subject will be considered as having a sustained reduction of OCS Dose.

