18.8.1.4 Corticosteroid usage, cumulative and average daily dose

The study protocol defines rules of CS usage during the study. The non-compliance with these rules will be described using data collected in “Concomitant Medications” eCRF form and

subjects' compliance with CS usage rules checked during the medical review and protocol deviation process (i.e. subjects with PD code = PDEV52e).

According to protocol secondary criterion the following criteria will be summarized:

- Cumulative prednisone-equivalent dose (mg) from baseline visit until end of 52-week treatment period. If one subject does not receive any CS between baseline and end of treatment period then his cumulative dose will be set to 0 mg.

Cumulative dose [mg] = sum of (dose per administration * daily dosing frequency * Duration),

with:

- Sum of () = sum of all CS recorded in Concomitant Medication eCRF form, from baseline visit until the end of 52-week treatment period
- Duration = End CS dose date during treatment period – Start CS dose date + 1
- Daily dosing frequency using frequency conversions (See [Table 49](#) and [Table 50](#)).

As CS usage has to be restricted to the period between screening visit and end of treatment period, the following specific rules will be applied only for the calculation of cumulative prednisone-equivalent dose:

- Start CS dose date:
 - If start dose date is before screening date, baseline visit date will be considered as the start date for duration calculation.
 - If start dose date is after end of treatment period, CS will not be considered for duration calculation.
- End CS dose date:
 - If end is missing or after date of last IMP dose + 14 days or CS ongoing, the end CS dose date will be imputed by the last IMP dose date + 14 days for duration calculation. If last IMP dose is missing then end dose date will not be imputed and duration will not be calculated (patient not treated not taken into account in the analysis).
 - If end CS dose date is before baseline date, CS will not be considered
- Average daily steroid dose (mg) from baseline visit until end of treatment period. If one subject does not receive any CS between screening and end of treatment period then his average daily dose will be set to 0 mg.
 - Average daily dose [mg] = $\left(\frac{\text{Cumulative dose [mg]}}{\text{Duration}} \right)$
 - For completers, Duration = Week 52 date – baseline visit date + 1

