 - For discontinuers, Duration = Last IMP dose date + 14 – baseline visit date + 1

- If one subject does not receive any CS between baseline and end of treatment period then his daily dose will be set to 0 mg and change from screening value will be equal to 0 mg.
- Prednisone-equivalent daily dose [mg] by visit:
 - The prednisone-equivalent daily dose at visit X is calculated only if visit X is performed during treatment period (date of visit X \leq last treatment intake + 14 days).
 - At a scheduled visit, prednisone-equivalent CS daily dose is equal to the dose the subject is on at the scheduled visit. If several CS are taken at the same scheduled visit then all CS doses should be added. If a prednisone-equivalent CS dose stopped/changed at the scheduled visit date (Week X visit date), then the prednisone-equivalent CS dose started before (Week X visit date - 1 day) will be considered as the CS daily dose for that visit.
 - CS dose taken between two scheduled visits will not be taken into account in calculation of the scheduled-visit dose.
 - For subjects who completed the treatment period, CS dose that started on or after end of treatment will be excluded from the calculation.
 - All comparisons will be done compared to CS dosing at baseline. CS dosing at baseline is defined at CS dose taken the day of baseline visit (day 1). If patient did not receive any CS at baseline then CS dose is set to 0 mg.
 - For defining CS sparing effect endpoint (i.e. sustained reduction by W41 to Week 52), the derivation of prednisone-equivalent CS daily dose will be repeated at Week 40 scheduled visit using a different rule. If a prednisone-equivalent CS dose stopped/changed at the Week 40 scheduled visit date (Week 40 visit date), then the prednisone-equivalent CS dose started after (Week 40 visit date + 1 day) will be considered as the CS daily dose for that visit. Sustained reduction by Week 41 will be then programmed by checking that CS reduction is maintained between this new post-Week 40 (=Week 41) visit and Week 52 visit (i.e. CS dose at Week 52 is less or equal than CS dose at Week 41). The associated conditions related to CS sustained reduction (i.e. CS dose \leq 7.5 mg/day and \leq Day 1 CS dose, CS dose reduction from baseline \geq 25% and CS dose \leq 7.5 mg/day) will be checked for Week 41, 44, 48 and 52 visits.

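### Cumulative steroid dose is compared by a Wilcoxon test without baseline dose: a valid test, but one that gives up precision and is exposed to chance imbalance in starting dose

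*SAP*

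**What the plan says.** **Test.** Section 14.3.5 gives the comparison of cumulative dose in one sentence: "Cumulative prednisone-equivalent CS dose will be compared between placebo arm and evobrutinib arms with a pairwise non-parametric Wilcoxon rank sum test". It names no covariate and no stratum. The outcome is on the raw scale ("absolute value only) will be described using summary statistics"). Of the four endpoints in that section, this is the only one with a specified between-arm test.

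**Outcome.** Appendix 18.8.1.4 defines "Cumulative dose [mg] = sum of (dose per administration * daily dosing frequency * Duration"), summed from the baseline visit to the end of the 52-week period. For steroids already running at entry the rule is: "If start dose date is before screening date, baseline visit date will be considered as the start date for duration calculation". Subjects with no steroid over the period are set to 0 mg.

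**Baseline dose.** The same appendix fixes it: "CS dosing at baseline is defined at CS dose taken the day of baseline visit (day 1"), with 0 mg if none. Table 12 in Section 11.2.1 tabulates it as a continuous variable ("Prednisone-equivalent CS daily dose (Baseline")) and in categories, the first of which splits at 7.5 mg/day.

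**Steroid-sparing SRI endpoints.** Table 19 in Section 14.3.1 lists three, for example "SRI-4 Response at Week 52 with a Sustained Reduction of OCS Dose to 7.5 milligrams prednisone-equivalent per day or less" and not above the Day 1 dose during Weeks 41 to 52. They use the primary method of Section 14.1.2.1: logistic regression on treatment, race, screening SLEDAI-2K category and region. Steroid dose is neither a covariate nor a randomisation factor.

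**Contrast.** The HRQoL models in Section 14.3.4 adjust for baseline value and strata. The flare analyses (Sections 14.2.2.2 and 14.3.2.2) adjust for strata.

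**The concern.** A subject who enters on a given daily dose and stays on it accumulates that dose times the days on treatment. A subject who enters on none and stays on none scores zero. The starting regimen is therefore a component of the outcome, not merely a correlate of it. A test that ignores it treats differences present before the first tablet as noise. If one arm happens to start on more steroid, that difference enters the comparison and can imitate or mask steroid sparing.

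The SRI endpoints with sustained OCS reduction raise a milder form of the same point. A subject at or below 7.5 mg/day on Day 1 meets the steroid part by not increasing, while one above 7.5 mg/day must taper. The model does not separate the two groups.

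Steroid use is a stated secondary objective, so its one tested endpoint should be analysed efficiently.

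**Working it through.** **1. The plan's own figure.** Section 8.2.1 states 80% power with 103 evaluable subjects per arm for at least one of the two primary endpoints, each at 0.0125 one-sided. Simulation with SRI-6 responders nested in SRI-4 responders gives 81.7%. With a 20-point SRI-6 improvement it gives 77.4%, against 76% stated. The sample size reproduces. The SAP gives no power, SD or correlation for any steroid endpoint, so everything below rests on assumed values.

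**2. Cumulative dose: power.** Let ρ be the correlation of baseline with cumulative dose, δ the shift in SD units and n the number per arm. Assumptions: normal data, constant shift, two-sided 0.05.

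- Wilcoxon: power ≈ Φ(δ√(n/2 × 3/π) − 1.96)
- Baseline-adjusted: divide the first term by √(1 − ρ²)

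With n = 108 and δ = 0.25, the first term is 0.25 × √(54 × 0.955) = 1.795, so Wilcoxon power is Φ(−0.165) ≈ 43%. Adjusted at ρ = 0.5: 1.795/0.866 = 2.07, giving Φ(0.11) ≈ 54%. Simulation agrees to within about 2 points:

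| ρ | n = 108, δ = 0.25: Wilcoxon → rank ANCOVA | n = 103, δ = 0.39: Wilcoxon → rank ANCOVA |
|---|---|---|
| 0.3 | 44% → 47% | 76% → 80% |
| 0.5 | 42% → 53% | 77% → 87% |
| 0.7 | 45% → 69% | 79% → 97% |

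The Wilcoxon column should not vary with ρ; its spread is Monte Carlo error. The gain is about 3 to 4 points at ρ = 0.3, 10 at 0.5, and 18 to 24 at 0.7. Equivalently, 108 adjusted subjects per arm do the work of 108/(1 − ρ²) unadjusted: 108/0.75 = 144 at ρ = 0.5 and 108/0.51 = 212 at ρ = 0.7.

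**3. Cumulative dose: error rate.** With no treatment effect, simulated type I error of the Wilcoxon test was 4.2% to 6.1%, which is nominal. Conditional on a baseline imbalance of k standard errors, the test statistic has mean ρk and SD √(1 − ρ²) (normal approximation). At k = 1.96 and ρ = 0.5, the upper tail is 1 − Φ((1.96 − 0.98)/0.866) = 1 − Φ(1.13) ≈ 13%. The same formula gives 21% at ρ = 0.7 and 33% at ρ = 0.9. At k = 0 it gives 2.4% at ρ = 0.5 and 0.6% at ρ = 0.7. Averaged over randomisations this is 5%; given the imbalance actually drawn, it is not.

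**4. Steroid-sparing SRI, all subjects.** Assumptions: half the subjects start at ≤7.5 mg/day, conditional OR 2.25, 108 per arm, placebo response 40% in low starters. With 15% in high starters:

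- Pooled rates are (0.40 + 0.15)/2 = 0.275 on placebo and (0.600 + 0.284)/2 = 0.442 on active treatment. The pooled OR is 2.09.
- Unadjusted: ln(2.09)/0.290 − 1.96 = 0.58, power 72%.
- Adjusted: ln(2.25)/0.306 − 1.96 = 0.69, power 76%.

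With 25% in high starters the change is 80% to 81%; with 10% it is 65% to 71%. A second set (OR 2.4, 103 per arm, high-starter response 20%, 10% or 5%) gives gains of about 2, 7 and 11 points. The range is about 1 to 11 points, and the top needs a 40% versus 5% gradient.

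**The case against.** **The test is valid.** Randomisation protects it, and chance imbalance is what the 5% already covers. This stands. A reader might infer bias or an inflated error rate; step 3 of the working shows neither.

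**The steroid-sparing SRI endpoints do not ignore baseline dose.** This also stands. The Day 1 dose is a ceiling in the responder definition. It is missing only from the model, and the gain from adding it is small.

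**Baseline dose may not dominate.** A reader might infer from the formula that starting dose is the main source of variance. The documents do not quantify this. All systemic routes count, and accrual stops at last dose plus 14 days, so other sources contribute. Subjects at 0 mg cannot reduce, so the constant-shift simulations show direction and rough size only.

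**Other displays help.** The remaining Section 14.3.5 endpoints are relative to baseline, one is restricted to subjects at 7.5 mg or more at baseline, and Table 12 would show an imbalance. That is true, but none of these adjusts the one test specified. Sensitivity analysis 5 does not either: it adds immunosuppressants (ATC L04A), not corticosteroids (H02A), and only for the two primary endpoints. Some exploratory sections are redacted and cannot be checked.

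**Full stratification would be sparse.** Race × SLEDAI-2K category × region gives 2 × 2 × 3 = 12 cells, and the Japan cohort was planned at 36 subjects, or 9 per arm. This stands and shapes the fix.

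**Conclusion.** The point holds as one of efficiency and robustness. The Wilcoxon comparison of cumulative dose omits a baseline measure that the SAP already derives and that enters the outcome by construction. The cost is about 3 to 24 points of power for ρ from 0.3 to 0.7, plus sensitivity to whatever baseline imbalance was drawn. ρ, the effect size and the normal shape are assumptions. Below ρ of about 0.3 the gain is slight.

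The SRI part is secondary: about 1 to 11 points under assumed response rates and an assumed even split at 7.5 mg/day. These figures are for the all-subjects endpoint. The HDA endpoint has roughly half the subjects and was not computed, nor was the serologically active one.

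Under Section 14.3 all these p-values are nominal, and they lie outside the hierarchy of Section 14.1.2.4. No primary or key secondary conclusion is affected.

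**What to change.** **Main change, Section 14.3.5.** Compare cumulative dose by rank ANCOVA on baseline prednisone-equivalent daily dose (the Day 1 definition in Appendix 18.8.1.4), with race, screening SLEDAI-2K category and region as additive covariates rather than fully crossed strata. A van Elteren test stratified by baseline dose category is an acceptable alternative.

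**Secondary change, Section 14.3.1.** Add baseline dose (≤7.5 vs >7.5 mg/day, as in Table 12) to the logistic models for the SRI endpoints with sustained OCS reduction. Check for sparse cells in the HDA and serologically active subgroups, since Section 14.1.2.1 already foresees convergence trouble from zero cells.

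**Status and cost.** No new data and little code are needed. Sections 6.3 and 6.4 record that the study was terminated after review of the primary results, and version 4.0 postdates that review. Keep the planned analyses, report the adjusted ones beside them as supplementary, and label them post hoc, as Section 4 requires for unplanned analyses.

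### The between-arm test of cumulative steroid dose makes no allowance for follow-up, so if drop-out is unequal the arm with more of it tends to look steroid-sparing

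*SAP*

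**What the plan says.** Section 14.3.5 describes the total on its raw scale: "Cumulative prednisone-equivalent CS dose from Baseline until completion of the Treatment Period (absolute value only) will be described using summary statistics". It then assigns a test to it: "Cumulative prednisone-equivalent CS dose will be compared between placebo arm and evobrutinib arms with a pairwise non-parametric Wilcoxon rank sum test".

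Appendix 18.8.1.4 gives the derivation: "Cumulative dose [mg] = sum of (dose per administration * daily dosing frequency * Duration", summed over steroid records. For a steroid that is ongoing, has no end date or ends later than the cut-off, "the end CS dose date will be imputed by the last IMP dose date + 14 days for duration calculation". Appendix 18.8.1.1 leaves out steroids started on or after the end of treatment.

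The same appendix lists a time-normalised measure to be summarised: "Average daily steroid dose (mg) from baseline visit until end of treatment period", equal to cumulative dose divided by duration. Its denominator differs by group. "For discontinuers, Duration = Last IMP dose date + 14 – baseline visit date + 1". "For completers, Duration = Week 52 date", less the baseline visit date, plus one day. No test is assigned to this average.

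For the steroid-reduction responder endpoint in section 14.3.5, the rule is: "Subjects withdrawing from treatment before Week 40 or with missing data at Week 40 will be considered as non-responders".

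**The concern.** A total in milligrams grows with the number of days over which it is counted. Two subjects on the same daily dose get very different totals if one stops early, and the rank test reads the shorter record as lower steroid use. No rule in the SAP normalises, extrapolates or censors the totals, or gives early discontinuers an unfavourable rank.

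Elsewhere the plan does deal with unequal follow-up. The flare-rate model has an offset for log exposure time (section 14.3.2.2), and adverse events get exposure-adjusted rates (section 15.1.1.3). Within section 14.3.5 itself, early withdrawal counts against a subject on the responder endpoint and in the subject's favour on the cumulative total.

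What is at stake is the reading of the only test of steroid amount as such. A difference in time on treatment, for example from safety stops in one arm, could appear as a steroid-sparing effect.

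**Working it through.** The SAP states no figure for this comparison, so there is none to reproduce.

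**Step 1: the derivation applied to single subjects** (continuous steroid, baseline on Day 1)

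- 10 mg/day, last study dose on Day 56: 10 × (56 + 14) = 700 mg.
- 10 mg/day, completer counted over 365 days: 10 × 365 = 3,650 mg.
- 20 mg/day, last study dose on Day 60: 20 × (60 + 14) = 1,480 mg.

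The third subject takes twice the daily dose of the second but ranks as the lower user. Divided by their own durations, the three give 700/70 = 10, 3,650/365 = 10 and 1,480/74 = 20 mg/day, which is the right order.

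**Step 2: effect on the test when the arms do not differ**

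Inputs from the SAP: about 108 subjects per arm (section 8.2.1), two-sided 5% level (section 14.3), cut-off at last dose + 14 days (appendix 18.8.1.4).

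Assumptions, not from the SAP: the same dose distribution in both arms (15% on 0 mg, the rest log-normal with median 10 mg/day and log-SD 0.6), each subject's dose constant over time, last-dose day of drop-outs uniform over days 1 to 364, and the drop-out rates below. Total = daily dose × 365 for completers, or × (last-dose day + 14) for drop-outs. There were 4,000 simulated trials per row.

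| Drop-out, placebo / active | Total dose: rejects | of which favouring active | Daily dose: rejects |
|---|---|---|---|
| 20% / 20% | 5.2% | 2.6% | 5.1% |
| 15% / 20% | 5.8% | 4.5% | 5.1% |
| 15% / 25% | 8.3% | 7.5% | 5.3% |
| 15% / 30% | 11.6% | 11.0% | 4.8% |
| 15% / 35% | 15.4% | 15.3% | 4.9% |
| 10% / 30% | 15.8% | 15.6% | 5.1% |
| 20% / 40% | 16.2% | 15.9% | 5.5% |
| 25% / 15% | 8.1% | 0.5% | 4.4% |

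At 15% / 30% the average median totals are 2,934 and 2,649 mg. The apparent saving is (2,934 − 2,649)/2,934 = 9.7% with identical daily doses. The last row shows the direction reversing when placebo has more drop-out.

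**Step 3: other assumptions**

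With 117 per arm (469/4 = 117.25 from section 8.2.2) and a median of 8 mg/day, rejection was 5.0% at 15/15, 11.1% at 15/30, 11.7% at 20/35 and 17.2% at 20/40. The daily-dose test stayed at 4-6%. Repeat runs under these assumptions gave 5.5% at a 5-point gap, 8.9% at 10 points, 12% at 15/30 and 17% at 20/40.

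**Step 4: does the average hold up if doses fall over time?**

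Constant doses flatter the average, so tapering was tried. With a 30-50% taper by Week 40 the average-dose test rejects 5-6% of the time. With a 70% taper it reaches about 7% at a 15-20-point gap, leaning against the arm with more drop-out.

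**Step 5: the completer window of the average**

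The appendix describes the sum as running to the end of the 52-week treatment period, but its cut-off rule allows last study dose + 14 days. The completer denominator stops at Week 52. At most, the average is too high by 14/365 = 3.8% (10 mg/day would become 10 × 379/365 = 10.38). For discontinuers both periods end at last dose + 14 days.

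**The case against.** The strongest reply is that the consequence is small and conditional. This is an other secondary endpoint with nominal p-values (section 14.3), outside the testing hierarchy (section 14.1.2.4). Average daily dose is to be summarised and dose by visit is described, so time-normalised figures stand beside the test. Table 1 lists cumulative dose as the endpoint, so moving the test changes what is tested. Version 4.0 was also written after the primary-analysis results had been reviewed. All of this stands; it limits the weight of the point and shapes the fix, but does not make the total comparable across unequal follow-up.

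Four stronger readings are tempting, and the SAP does not support them:

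- *Drop-outs rank lowest.* Subjects with no steroids score 0 mg and rank below them. Drop-outs on steroids move down, not necessarily to the bottom.
- *No other test touches steroid use.* Table 19 tests SRI composites that require a sustained low oral steroid dose, and these count a missing Week 52 response as non-response, so they penalise drop-out.
- *The p-value measures time on study rather than steroid use.* Even at the largest rate found, 17.2%, the test does not reject about 83% of the time, and at equal drop-out with the same timing it keeps its level.
- *Section 7 shows the bias is present.* It says only that drop-out may be higher than expected. Higher is not unequal, and no rate by arm is given.

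**Conclusion.** The point holds in conditional form. The tested total is not adjusted for follow-up, and no other rule in the SAP corrects this. Bias between arms needs unequal drop-out or unequal timing. Under the stated assumptions the false-positive rate is about 5% with equal drop-out, 6% at a 5-point gap, 8-9% at 10 points, 11-12% at 15 points and 15-17% at 20 points, with the excess favouring the arm with more drop-out. The drop-out rates, dose distribution and timing are assumed, so these figures show a range and do not estimate what happened in this trial.

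The average daily dose is the better variable but is not free of bias under strong tapering. The completer mismatch is an internal ambiguity of at most 3.8%. It applies to completers in every arm and affects only a descriptive variable as the plan stands. No primary or key secondary conclusion is affected.

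**What to change.** 1. Reconcile appendix 18.8.1.4 so that the numerator and denominator of the average daily dose cover the same days for everyone: either both end at the earlier of Week 52 and the last study dose, or both include the extra 14 days.
2. Run the Wilcoxon comparison on that average. In a plan fixed before results are seen, it can replace the test on the total. Sections 6.3 and 6.4 say the primary-analysis results had been reviewed, so here it should be added as a clearly labelled sensitivity analysis and identified in the study report as section 4 requires for unplanned analyses.
3. Keep cumulative dose as the listed endpoint, summarised with follow-up time by arm and separately for completers. Where its p-value is reported, note that it is not adjusted for time on study.

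The cost is a few lines of SAP text and one more test on a variable already specified. The downsides are that averages from short follow-up are noisier yet count equally, and that under strong tapering the average leans slightly against the arm with more drop-out.
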